2 STUDY OBJECTIVES

2.1 Primary Objective

This is a prospective, nonrandomized, sequential data collection study to evaluate the ability of RPVi to predict fluid responsiveness in comparison with other dynamic parameters including SVV and/or PPV. Although this is a non-interventional study, focused on data collection, patients will be assigned to one of the two study groups with different tidal volumes: 6 ml/kg IBW and 8 ml/kg IBW. The research data will not be used to modify the subject's standard of care.

Specific aims:

- Evaluate the clinical utility of the RPVi as a predictor of fluid responsiveness in mechanically ventilated patients at two specific tidal volumes (6 ml/kg IBW and 8 ml/kg IBW).
- Characterize the correlations between the RPVi and PPV and/or SVV, as measured by FDA cleared comparator systems, as predictors of fluid responsiveness at two specific tidal volumes (6 ml/kg IBW and 8 ml/kg IBW).

Hypothesis (constructed as the null):

- RPVi as a dynamic monitor of cardiac function will not predict a subsequent increase in cardiac output following the administration of a fluid bolus of a crystalloid solution at a tidal volume of either 6 or 8 ml/kg IBW in intubated, mechanically ventilated patients.

- Changes in RPVi will not differ from concurrent changes in PPV and/or SVV, as measured by FDA cleared comparator systems following the administration of a fluid bolus of a crystalloid solution at a tidal volume of either 6 or 8 ml/kg IBW in intubated, mechanically ventilated patients.

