4 SUBJECT SELECTION AND WITHDRAWAL

4.1 Number of Subjects

There will be up to 150 subjects enrolled into this study, divided into two groups. There will be no protocol or procedural differences between the groups. The first group of up to 100 subjects will be used to gather data to determine the thresholds for fluid responsiveness that would be used for the second group of 50 subjects. The second group will be the validation set to be used to evaluate study objectives. The anticipated duration of subject participation in this study will not exceed 1 visit. The study enrollment period is expected to be approximately 2 years.

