8 STATISTICAL PLAN

Prior studies of the predictive abilities of dynamic monitors of cardiac function with respect to cardiac output have established that sample sizes of 50 patients are sufficient to characterize the performance of the monitor. However, based on an ongoing Masimo study at another clinical test site, preliminary data received suggests that, of the first 83 subjects enrolled approximately 29% were responders. Therefore, in order to analyze the ability of RPVi, the sample size will be increased to a total of up to 150 patients. The first group of up to 100 subjects will be used to gather data to determine the thresholds for fluid responsiveness that would be used for the second group of 50 subjects. The second group will be the validation set to be used to evaluate study objectives in **section 2.1**. As such, the study will be registered on ClinicalTrials.gov but only results from the validation phase will be posted.

Normality of distribution will be tested before any statistical evaluation by using the Kolmogorov- Smirnov method. Descriptive statistical data will be reported as mean \pm SD. Except for the bias between both methods (RPVi vs PPV/SVV and SV/CO measurements). Comparisons between PPV/SVV and RPVi and between CO/SV measurements will be performed with a paired student t test. PPV/SVV and RPVi as well as SV/CO measurements will be compared using Bland and Altman. In order to evaluate the ability of RPVi to reliably detect changes in PPV/SVV and for CO measurements to accurately track Flotrac CO changes we will use a method based on polar plotting of PPV/SVV and RPVi and CO measurements changes over consecutive cycles as described by Critchley et al. We will exclude from this analysis small changes of mean value of

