PPV/SVV and RPVi and CO measurements less than 3%. In this method, a good trending ability requires an angular bias no greater than ± 5 degrees and a SD for the polar angle of less than ± 15 degrees. In this method, simultaneous changes of each indices of consecutive validated respiratory cycle will be reported on a polar plot. The polar angle will be derived from the ratio of the changes of the two indices such a ratio close to one led to a null angle with the x axis, this angle approach a 90 degrees angle when the ratio diverges from one. The radius will be the mean of the simultaneous changes of the two indices between two consecutive validated respiratory cycles. In these conditions a mean angle and its SD can be calculated.

The strength of linear dependence between PPV/SVV and RPVi and SV/CO measurements for all patients will be measured by the Pearson coefficient of correlation. The mean of correlation coefficients and comparison between correlation coefficients will be performed after a Fischer's transformation. In order to analyze the ability of RPVi to correctly classify the respiratory cycle as responder or non-responder after a volume loading in respect to a theoretical threshold value of PPV/SVV of 12%, we will measure the area under the curve of a Receiver Operating Characteristic (ROC) curve. Then the selected value of RPVi for each patient will be the one which maximized the Youden index (sensitivity + (specificity - 1)). The agreement between the two classifications will be quantified by the Kappa score for each patient, taking as threshold value of RPVi the individual value determined by the ROC curve. The reported mean values of areas under ROC curves and Kappa scores will be therefore calculated from the individual values. Taking the intra patients coefficient of correlation as a dependent variable, we will estimate its relationship with potentially explanatory variables by using univariate analysis, including Student t test for qualitative data and correlation for quantitative data and multivariate analysis by multiple linear regression. Categorical binary variable will be transformed into dummy variables. Other correlations will be evaluated by Pearson coefficient.

For all comparisons, a P value < 0.05 will be considered significant. Statistical analysis will be performed using SPSS software version 13.0 for Windows (SPSS Inc., Chicago, IL).

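### Section 8 contains no analysis that scores a first-group RPVi threshold in the 50-subject validation group; its only RPVi cut-off is fitted and scored within each patient, which biases kappa upward

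*Combined protocol and SAP*

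**What the plan says.** Section 4.1 gives the first group (up to 100 subjects) the task to "determine the thresholds for fluid responsiveness that would be used for the second group of 50 subjects". Section 8 repeats this and adds: "The second group will be the validation set to be used to evaluate study objectives". It also says that "only results from the validation phase will be posted".

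The analyses that follow in section 8 are a normality test, paired t tests, Bland-Altman, polar plots, Pearson correlations, an ROC analysis, kappa, and a regression on the intra-patient correlation. After the two groups are introduced, neither is named again.

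The ROC analysis classifies respiratory cycles "in respect to a theoretical threshold value of PPV/SVV of 12" per cent. Then "the selected value of RPVi for each patient will be the one which maximized the Youden index", and kappa is computed for each patient, "taking as threshold value of RPVi the individual value determined by the ROC curve". Finally: "The reported mean values of areas under ROC curves and Kappa scores will be therefore calculated from the individual values".

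The first null hypothesis in section 2.1 concerns something else, namely that RPVi "will not predict a subsequent increase in cardiac output following the administration of a fluid bolus of a crystalloid solution".

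**The concern.** A threshold re-fitted in every patient is not one carried over from another group, so the ROC and kappa text cannot serve as the missing validation step. Four things follow.

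- **No validation figure.** Followed as written, the posted results contain no sensitivity, specificity or agreement for a pre-set RPVi threshold, which is what the split into two groups is for.
- **Optimistic kappa.** The cut-off is chosen and scored on the same cycles. A personal cut-off also absorbs any patient-to-patient offset in RPVi, which a user with a new patient could not do.
- **Undefined patients.** If all of a patient's cycles lie on one side of 12%, there is no AUC, cut-off or kappa. The reported means then cover an unstated subset.
- **Different reference.** Even a locked threshold scored against PPV/SVV of 12% would not test prediction of a cardiac output rise.

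AUC, correlation, Bland-Altman and polar plots use no RPVi cut-off, so the cut-off optimisation does not affect them.

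**Working it through.** **Figures from the plan.** Section 8: up to 100 + 50 = 150 subjects; about 29% responders in preliminary data from another site; PPV/SVV reference 12%. The sum agrees. The sample size itself cannot be reproduced, because no target AUC, sensitivity, specificity, kappa, precision or power is given. Cycles per patient and the spread of PPV and RPVi are not given either, so every value for them below is an assumption.

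**Direction of the bias.** For one patient with a share p of cycles above 12%, let J = sensitivity + specificity − 1. With observed agreement po and chance agreement pe, kappa = (po − pe)/(1 − pe), and po − pe = 2p(1 − p)J. Kappa therefore has the sign of J. The extreme cut-offs give J = 0, so the maximised J is never negative, and neither is the kappa computed on the same cycles. If RPVi carries no information, true kappa is 0 but the average of these values is above 0.

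**Size with uninformative RPVi.** Independent cycles, 4,000 simulated patients per setting, 29% of cycles positive:

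| Cycles per patient | Mean own-cut kappa (truth 0) |
|---|---|
| 20 | 0.23 |
| 40 | 0.17 |
| 120 | 0.10 |

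At 20% or 50% positive the values are 0.22–0.24, 0.16–0.17 and 0.10–0.11. The bias shrinks with more cycles: about 0.08 at 200, 0.05 at 500 and 0.04 at 1,000.

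**Own cut against locked cut.** Patient PPV mean ~ N(10, SD 4), plus N(0, SD 2) per cycle; RPVi = PPV + patient offset + N(0, SD 1.5); 40 cycles. The locked cut is the Youden cut over the cycles of 100 other patients. Own-cut and locked-cut kappas are averaged over the same patients, those with cycles on both sides of 12%.

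| Offset SD | Own cut, same cycles | Own cut, new cycles | Locked cut |
|---|---|---|---|
| 0 | 0.64 | 0.46 | 0.50 |
| 2 | 0.64 | 0.46 | 0.36 |
| 4 | 0.64 | 0.46 | 0.23 |
| 6 | 0.64 | 0.46 | 0.16 |

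Optimism is the step from the first kappa column to the second: 0.64 − 0.46 = 0.18. The step from the second to the third is transfer. At SD 6 it is 0.46 − 0.16 = 0.30; at SD 0 the locked cut does slightly better than a noisy personal one. A PPV mean of 11 changes the own-cut and locked-cut values by at most 0.01.

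**A second model.** Binormal RPVi with within-patient AUC 0.5, 0.7 or 0.8 and 10 to 200 cycles also gave upward bias in every scenario. With between-patient spread of one within-patient SD and AUC 0.7 or 0.8, own-cut kappa still exceeded locked-cut kappa by about 0.12 to 0.16 at 200 cycles.

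**Undefined patients.** With the same between-patient SD of 4, PPV mean 10 and 40 cycles, the share of patients entirely on one side of 12% is 63%, 35% and 17% at within-patient SD 1, 2 and 3. Over PPV means 8 to 12 it runs from 74% to 13%.

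**Precision of the repaired analysis.** 0.29 × 50 = 14.5 expected responders. Exact 95% intervals: sensitivity 12/15 = 0.80 (0.52–0.96); specificity 28/35 = 0.80 (0.63–0.92).

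**The case against.** The strongest reply is that section 8 does state the development-and-validation intent, so only the scoring step is unwritten. That is accurate, but the rule that is written conflicts with the intent, so this is more than missing detail. Section 8 also does not say that the thresholds are RPVi thresholds. If they are not, no RPVi threshold is set for validation at all, and the gap remains.

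Three limits on size stand.

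- Section 8 does not say which group the per-patient kappa covers. If it is used only in the first group, the inflated kappa is not a posted result, but the posted results then contain no figure at any RPVi cut-off.
- Arterial waveforms are captured at high speed (sections 6.2 and 10.5), so cycles per patient may be many and the overfitting small. Serial correlation between cycles would work the other way.
- The undefined shares assume stable PPV. If 20 cycles before and 20 after the bolus are pooled and PPV falls 3 points around an overall mean of 10, they drop to about 46%, 25% and 13%. A 5-point fall gives about 33%, 17% and 9%. The plan does not settle which cycles are used.

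Section 3 was not available to this review and the bolus and measurement timing in section 7 are redacted, so a responder definition may exist elsewhere. The claim is confined to section 8.

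**Conclusion.** The concern holds and should be fixed before second-group data are analysed, because a threshold cannot credibly be called pre-set afterwards. Three parts rest on the text alone: no listed analysis applies a first-group RPVi threshold to the validation group, the only RPVi cut-off is fitted and scored in the same patient, and the reference is not the outcome in the hypothesis.

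The upward direction of the kappa bias is firm. Its size is illustrative: roughly 0.1 to 0.2 at 20 to 120 independent cycles when RPVi is uninformative, and less with more cycles. The larger gaps between own and locked cut-offs (up to 0.64 against 0.16) are mostly failure to transfer under assumed offsets and should not be read as the size of the bias.

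**What to change.** In section 8:

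1. Derive the RPVi threshold(s) once across first-group patients, per tidal volume if that is intended, and record them before second-group data are analysed.
2. Apply them unchanged to one pre-bolus RPVi value per second-group patient.
3. Score them against a stated responder definition based on the change in cardiac output or stroke volume. Section 7 already collects these before and after volume expansion, so no new measurement is needed.
4. Report sensitivity, specificity and predictive values with confidence intervals.
5. Keep the per-patient Youden and kappa analysis against PPV/SVV of 12% as exploratory agreement only. Name the group and the cycles it covers, and report how many patients drop out because their cycles never straddle 12%.

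The cost is SAP wording and minor analysis work. Agreement at a locked threshold will probably look lower than the own-cut kappa. With about 14 or 15 responders the intervals will be wide, and wider still if split by tidal volume; the plan should say so in advance.

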RPVi reflects measurements of ventilation induced respiratory changes in Pi over a period of time and is calculated as follows:

$$PVi \text{ or } RPVi = [(Pimax - Pimin)/Pimax] \times 100(%)$$

Multiple studies have demonstrated that PVi can predict fluid responsiveness in mechanically ventilated patients (Desebbe 2010) and can be used to optimize intraoperative fluid therapy (Desebbe 2008). Yin and Ho (2012) and Sandroni (2012) have provided meta-analyses confirming the clinical utility of PVi to guide clinical care. Among the available dynamic monitors of cardiac function in common clinical use (pulse pressure variation PPV, stroke volume variation SVV, corrected esophageal Doppler flow time FTc, etc.) the respiratory variations in the pulse oximeter plethysmographic waveform amplitude (pleth variability index PVi) has the advantage of being completely non-invasive.

The sensitivity of a dynamic monitor of cardiac function is dependent on the magnitude of the swings in the intrathoracic pressure associated with mechanical ventilation. During the introduction of these monitors into daily anesthetic management there has been a concurrent evolution in our intra-operative ventilator management protocols. During the past decade of practice, commonly recommended intraoperative tidal volumes have declined from 10 ml/kg to 8 ml/kg and now down to 6 ml/kg. Recommendations for the use of dynamic monitors as a guide for intraoperative fluid management stress that positive studies were done with controlled tidal volumes of 8 ml/kg and their sensitivity has not been established under conditions

including smaller tidal volumes. There is a pressing need to re-evaluate the performance and utility of these monitors under currently recommended respiratory management practices.

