The evolution of the pulse oximetry sensors to incorporate multi-wavelength technologies provided the opportunity to modify the PVi algorithm and improve clinical performance. As a dynamic monitor of cardiac function, PVi/ RPVi is analogous to pulse pressure variation (PPV), which may be derived through minimally-invasive means using beat-to-beat arterial pressure expressed as a percentage by the Philips IntelliVue (Philips Labs, Noord Brabant, NL) or stroke volume variation (SVV), which may be derived through minimally-invasive means using pulse contour analysis of the arterial pressure waveform as done by the Vigileo/Flotrac System (Edwards Labs, Irvine, CA) or Philips IntelliVue (Philips Labs, Noord Brabant, NL). Multiple studies have demonstrated that PPV and/or SVV is a valuable tool in predicting fluid responsiveness in mechanically ventilated patients.

The aim of this study is to test the ability of RPVi to predict fluid responsiveness in mechanically ventilated patients in the operating room and to compare it to other dynamic monitors of cardiac function in this setting.

This study will include patients [REDACTED] undergoing cardiac surgical procedures in which pulmonary and peripheral arterial catheters are standard monitors used for continuous monitoring of cardiac function and blood pressure, respectively. Patients with cardiac arrhythmias and intracardiac shunts will be excluded. Patients will be assigned to one of the two study groups with different tidal volumes: 6 ml/kg IBW and 8 ml/kg IBW. Both tidal volumes are within the range that is commonly used intra-operatively. In patients without significant pulmonary disease there is no significant risk or benefit associated with either tidal volume, however, there is evidence of decreased utility of the dynamic monitors of cardiac function (PPV/SVV) at lower tidal volumes. Attention to the tidal volume will aid the assessment of the utility of RPVi as a monitor of cardiac response to fluid administration.

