7 STUDY PROCEDURES

- Patients are assigned to be ventilated in a volume controlled mode with a tidal volume of either 6 or 8 $\text{ml} \cdot \text{kg}^{-1}$ of ideal body weight (Devine formula) at a frequency [REDACTED]. Positive end-expiratory pressure is to be set [REDACTED] according to the attending physician.
- Anesthesia is induced as per standard of care. Radial and pulmonary arterial catheters inserted as per standard of care.
- All required sensors are placed as per the corresponding instructions for use for the various measurements
- All patients are to be studied [REDACTED] with no changes in anaesthetic protocol and no volume expansion. Unless clinically contraindicated, patients will receive an intravenous volume expansion consisting of [REDACTED] given over [REDACTED].
- Baseline set of haemodynamic measurements (stroke volume and or cardiac output) are to be performed prior to the intravenous volume expansion.
- A repeat set of hemodynamic measurements are to be performed [REDACTED] after volume expansion.

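### Both aims are set at 6 and 8 ml/kg IBW, but section 8 specifies no RPVi result by tidal volume, and for aim 1 no ROC against cardiac output or stroke volume response at all

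*Combined protocol and SAP*

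**What the plan says.** Section 2.1 asks, as aim 1, for RPVi to be evaluated "as a predictor of fluid responsiveness in mechanically ventilated patients at two specific tidal volumes", namely 6 and 8 ml/kg IBW. Aim 2 asks for the correlation of RPVi with PPV and/or SVV at the same two volumes. The first null hypothesis is that RPVi "will not predict a subsequent increase in cardiac output following the administration of a fluid bolus of a crystalloid solution at a tidal volume" of 6 or 8 ml/kg IBW. The second, on changes in RPVi against changes in PPV/SVV, is tied to the same volumes.

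Section 7 puts this into the design: "Patients are assigned to be ventilated in a volume controlled mode with a tidal volume of either 6 or 8" ml/kg of ideal body weight. Section 1.1 gives the reason. For dynamic monitors in general, "positive studies were done with controlled tidal volumes of 8 ml/kg and their sensitivity has not been established" at smaller volumes. It adds: "Attention to the tidal volume will aid the assessment of the utility of RPVi as a monitor of cardiac response to fluid administration".

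Section 8 divides patients only into a threshold-setting group (up to 100) and a validation group (50). Of the latter it says: "The second group will be the validation set to be used to evaluate study objectives in" section 2.1. It then lists paired t tests, Bland-Altman analysis, polar plots, a Pearson correlation described as covering all patients, and a ROC analysis that classifies respiratory cycles against PPV/SVV at 12%. An RPVi cut-off is chosen within each patient by the Youden index. The summary is: "The reported mean values of areas under ROC curves and Kappa scores will be therefore calculated from the individual values". A last model regresses the intra-patient correlation coefficient on explanatory variables that are not named.

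**The concern.** Tidal volume is part of the stated question, yet an analyst could follow section 8 exactly and report nothing at 6 or at 8 ml/kg. Section 8 also says that only validation-phase results will be posted. The posted results could then leave aim 1 unanswered at either volume, or by-volume results could be added once the data are known. If only overall summaries appear, any difference in RPVi performance between the volumes would not show, including at the smaller volumes for which section 1.1 says that performance is not established.

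**Working it through.** **1. The plan's own figures.** 100 + 50 = 150, as stated. The 29% responder rate fits 24/83 = 28.9%. The 50 for validation cannot be re-derived: section 8 gives no power, target AUC or precision, and the text I could see gives no allocation ratio between volumes.

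**2. Objectives against analyses.**

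| Section 2.1 asks for | Section 8 specifies | By volume? |
|---|---|---|
| Aim 1 and hypothesis 1: RPVi predicts the response to the bolus at 6 and 8 ml/kg | Per-patient ROC and kappa for respiratory cycles, reference PPV/SVV 12% | No; nor is there a ROC against CO/SV response for all patients |
| Aim 2: RPVi correlation with PPV/SVV at 6 and 8 ml/kg | Pearson correlation over all patients; averaging and comparison of coefficients; model of the intra-patient correlation | Only if tidal volume is one of the unnamed variables |
| Hypothesis 2: changes in RPVi v PPV/SVV at 6 and 8 ml/kg | Paired t test, Bland-Altman, polar plot | No |

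The aim 1 gap thus has two parts: no result by volume, and no ROC against the outcome named in the hypothesis. Splitting the ROC that is written would close only the first.

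**3. If the reported means pool the volumes.** Let w8 be the share of patients at 8 ml/kg, and A6 and A8 the mean per-patient AUC (or kappa) at each volume. Then

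overall mean = (1 - w8) x A6 + w8 x A8, so overall mean - A6 = w8 x (A8 - A6).

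Neither w8 nor the gap is given, so these are illustrations:
- w8 = 1/2: gaps of -0.10, 0, 0.10 and 0.20 shift the overall mean from the 6 ml/kg mean by -0.05, 0, 0.05 and 0.10.
- Gap 0.15: the shift runs from 0.05 (w8 = 1/3) to 0.10 (w8 = 2/3).

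**4. What reporting by volume would deliver.** This concerns the proposed analysis (one RPVi value and one CO/SV response per patient), not section 8 as written. Inputs: 50 validation patients and 29% responders (section 8); a 1:1 split and the AUCs are assumed.

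Responders: 50 x 0.29 = 14.5 overall and 25 x 0.29 = 7.25 per volume. Take 7 v 18 per volume, 14 v 36 overall.

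Hanley-McNeil variance: [A(1 - A) + (n1 - 1)(Q1 - A²) + (n0 - 1)(Q2 - A²)] / (n1 n0), with Q1 = A/(2 - A) and Q2 = 2A²/(1 + A). At A = 0.80, Q1 = 0.667, Q2 = 0.711 and A² = 0.64.
- Per volume: (0.16 + 6 x 0.0267 + 17 x 0.0711)/126 = 0.01213; SE 0.110; half-width 1.96 x 0.110 = 0.22.
- All 50: (0.16 + 13 x 0.0267 + 35 x 0.0711)/504 = 0.00594; SE 0.077; half-width 0.15.
- With 20% responders: 0.25 v 0.17. With 40%: 0.19 v 0.13.
- With an unequal 20/30 split at 29%: 0.24 and 0.19.

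Exact 95% CIs for example counts: sensitivity 5/7, 0.29 to 0.96 (10/14: 0.42 to 0.92); specificity 13/18, 0.47 to 0.90 (26/36: 0.55 to 0.86).

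Difference between volumes, AUC 0.80 v 0.65: the variance at 0.65 with 7 v 18 is 0.0167, so SE = √(0.0121 + 0.0167) = 0.170. Two-sided power at 0.05 is about 14%. With 14 v 36 per volume, as in a first group of 100 split 1:1, SE is 0.119 and power about 24%.

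**The case against.** The best defence is that section 8 takes in the objectives by reference, and those objectives name both volumes. It also says the first group will "determine the thresholds for fluid responsiveness that would be used for the second group of 50 subjects", and the plural leaves room for one threshold per volume. Tidal volume is a two-level assigned factor, so it is an obvious candidate for the model of the intra-patient correlation, which provides for t tests on qualitative factors and dummy coding. Each per-patient value belongs to one volume, so means by volume could be tabulated later without loss. And the text between sections 2.1 and 4, which I could not see, may cover the split or the reporting.

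Much of this stands. It makes the fault one of under-specification, what is lost is pre-specification rather than data, and aim 2 may be partly covered. But a reference to the objectives is not an analysis. The regression has a correlation coefficient as its outcome, so it cannot show how well RPVi predicts response, and a coefficient for volume is not an estimate at each volume.

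It is also fair that a by-volume split of the existing ROC would not answer aim 1, because its reference is PPV/SVV; hence the two-part statement above. Finally, estimates from about 7 responders will settle little. That argues for showing the intervals, not for leaving the results out.

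Three stronger readings are tempting and not supported:
- That section 8 plans to pool the volumes. It does not say either way for the AUC and kappa means.
- That overall means would flatter RPVi at 6 ml/kg. Section 1.1 reports lower utility at smaller volumes for PPV/SVV, not for RPVi. The planned AUC and kappa measure agreement with PPV/SVV, so if the reference weakens too, agreement could fall, rise or stay the same.
- That the plan nowhere provides results by volume. Only section 8 can be judged.

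**Conclusion.** The concern holds, limited to section 8. Objectives and hypotheses are stated at two tidal volumes, and the analysis section specifies no RPVi result at either. Aim 1 is not served: it lacks both a by-volume result and a ROC against CO/SV response. Aim 2 is partly served at most, and only if tidal volume enters the regression.

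The documents do not allow the effect on reported results to be sized. If means pool the volumes, the shift is w8 x (A8 - A6), which is zero if RPVi performs alike at both; size and sign are unknown. The precision figures are firmer, but rest on the 29% responder rate from another site, an assumed 1:1 split and assumed AUCs. This should be corrected before the validation data are analysed.

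**What to change.** In section 8, state that validation-group results will be given for 6 and 8 ml/kg IBW separately, beside the overall figures, with 95% CIs and the numbers of patients and responders at each volume:
- AUC, sensitivity and specificity of RPVi for CO/SV response, one value per patient, at the threshold fixed in the first group;
- the correlations of RPVi with PPV/SVV;
- the per-patient AUC and kappa means, if they are kept.

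Name tidal volume as an explanatory variable in the intra-patient correlation model. Label any 6-versus-8 comparison exploratory and nonrandomized.

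The cost is analysis wording; no patient or procedure changes. The downside is the wide intervals shown in the working, and power between volumes too low for more than description. The CO/SV ROC adds an analysis that section 8 does not now contain, and it is needed for aim 1 whether or not results are split by volume.

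### The mean per-patient AUC and kappa can be computed only for patients whose PPV/SVV crosses 12%, so they describe a subset selected by the comparator

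*Combined protocol and SAP*

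**What the plan says.** All of this is in section 8 (Statistical Plan) of the combined protocol and SAP.

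- The unit and task are to "correctly classify the respiratory cycle as responder or non-responder after a volume loading".
- The reference is "a theoretical threshold value of PPV/SVV of 12" percent.
- The accuracy measure: "we will measure the area under the curve of a Receiver Operating Characteristic (ROC) curve".
- The cut-off is individual: "the selected value of RPVi for each patient will be the one which maximized the Youden index".
- So is the agreement measure: "The agreement between the two classifications will be quantified by the Kappa score for each patient". It uses the RPVi cut-off from that same patient's ROC curve.
- The summary is an average over patients: "The reported mean values of areas under ROC curves and Kappa scores will be therefore calculated from the individual values".

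Sections 4.1 and 8 also say that a first group of up to 100 subjects will supply thresholds for use in the second group of 50, which is the validation set. Section 8 adds that only the validation results will be posted.

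The plan does not require a patient to have cycles on both sides of 12% and sets no minimum count per class. It does not say what happens to a patient with one class only, and it does not ask for the number of contributing patients to be reported. No pooled ROC is given as a fallback. No redaction falls in this part of the text.

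**The concern.** An ROC curve needs both reference classes. Here the classes are formed within one patient from that patient's own PPV/SVV readings. A patient whose PPV/SVV stays below 12% throughout has no positive cycles, and one who stays above has no negative cycles. Neither can supply any of the three quantities to be averaged.

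The means then rest on patients whose comparator lies near 12% or moves across it with the bolus. RPVi is judged on a set chosen by the index it is compared with, and the result can be read as applying to all 50 validation patients.

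Two further effects follow. The average gives a patient with one or two cycles in the smaller class the same weight as a well-balanced patient. And section 2.1 asks for an evaluation at each tidal volume, while section 1.1 says that these indices depend on intrathoracic pressure swings and are less useful at lower tidal volumes. The share of patients who cross 12% may therefore differ between the two groups, and a comparison of the groups would rest on differently selected patients.

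**Working it through.** The plan states no expected AUC, kappa or number of evaluable patients, so there is no figure to reproduce. The check has two parts: what the formulas return for a one-class patient, and how many patients that might be.

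**1. The formulas with one class empty**

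Let n1 and n0 be the numbers of cycles above and not above 12% in one patient, and R1 the sum of the RPVi ranks of the n1 cycles.

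- AUC = [R1 − n1(n1+1)/2] / (n1·n0). With 20 cycles all below 12%, n1 = 0 and n0 = 20, which gives 0/0.
- Youden index = sensitivity + specificity − 1. With n1 = 0, sensitivity has a zero denominator (with n0 = 0, specificity does), so no maximum exists and there is no cut-off.
- Kappa = (po − pe)/(1 − pe). The plan takes its cut-off from the patient's own ROC, so kappa cannot be formed. Suppose a cut-off were imported and a share q of cycles had RPVi above it. Then po = 1 − q and pe = 0·q + 1·(1 − q) = 1 − q. Kappa is 0/q = 0 if q > 0, and 0/0 if q = 0. It carries no information either way.

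This part needs no outside figure.

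**2. How many patients: illustration only**

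The documents give no PPV/SVV distribution, no within-patient variation, no fall after the bolus and no cycle count. Every input below is assumed.

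*Set A.* PPV/SVV mean 8, 10 or 12%; between-patient SD 4 or 5; within-patient SD 1 or 2; mean fall after the bolus 0 or 4 points; 40 cycles per patient, half before and half after. For RPVi, a patient-specific offset with SD 3 and a within-patient correlation of 0.5 with PPV beyond the shared fall. 1,500 simulated patients per scenario.

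*Set B.* At 8 ml/kg, PPV 14 ± 4% in 29% of patients and 8 ± 3% in the rest; values multiplied by 6/8 = 0.75 at 6 ml/kg; within-patient SD 1-2; a fall of 15-30% after the bolus in the first subgroup and half that in the other; 100 cycles. 20,000 simulated patients per scenario.

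| Assumptions | Not evaluable | Evaluable of 50 |
|---|---|---|
| Set A, all cycles | 21-76% | about 12-39 |
| Set A, cycles after the bolus only (between-SD 4, within-SD 1, fall 4) | 78-94% | about 3-11 |
| Set B, 8 ml/kg, all cycles | 32-62% | – |
| Set B, 6 ml/kg, all cycles | 53-80% | – |
| Set B, both groups, split 25/25 | – | about 15-29 |

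The last row is 25 × 0.38 + 25 × 0.20 = 14.5 at the low end and 25 × 0.68 + 25 × 0.47 = 28.75 at the high end. The even split is also an assumption.

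**3. Who is lost, and the quality of what remains**

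- In Set B the lost patients mostly stay below 12%. Those who stay above it throughout are 0.4-7.4% of patients at 8 ml/kg and at most 0.6% at 6 ml/kg.
- In Set A, 16-34% of the retained patients have at most two cycles in the smaller class (all-cycles scenarios), so their AUC and optimised cut-off are unstable.
- In the same scenarios the mean of individual AUCs is 0.76-0.92, and a pooled AUC over all patients' cycles is 0.86-0.94. With mean 8, between-SD 5, within-SD 1 and no fall, the values are 0.79 and 0.92. With mean 12, between-SD 4, within-SD 1 and a fall of 4, they are 0.92 and 0.90. These are different quantities and either can be the larger.

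**The case against.** The strongest reply is that the plan never says one-class patients are dropped. It is silent, so the defect could be called unspecified handling. That is fair as a description of the text, but the stated rule leaves no other outcome: there is no individual value to enter into the mean.

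A second reply is that section 8 names no primary endpoint. The hypothesis in section 2.1 concerns cardiac output, and the individual AUC and kappa sit beside Bland-Altman, polar-plot and correlation analyses. This stands. A reader might take these means as the headline result, and the documents do not say so. They are, however, the only analysis in section 8 that classifies responders and non-responders.

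A third reply is that a threshold carried over from the first group would classify every validation patient. That is so, and the fix below uses it. But section 8 does not reconcile that threshold with its individual cut-offs.

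Finally, the numbers have no documentary basis. This also stands. Neither range is an estimate for this trial, and the proportional scaling with tidal volume in Set B is an assumption. Section 1.1 gives a direction of reduced utility, not a ratio.

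**Conclusion.** The point holds as a matter of definition. For a patient whose PPV/SVV stays on one side of 12%, the planned AUC, cut-off and kappa do not exist, and the reported means cover only patients whose comparator crosses 12%. They would represent all 50 validation patients only if every one of them crossed, which the plan neither requires nor checks.

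The size of the loss is unknown. Under the assumptions shown, roughly 20-80% of patients are not evaluable when all cycles are used, and more if only cycles after the bolus count.

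Three stronger readings are tempting and not supported.

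- A reader might infer from the statement that "of the first 83 subjects enrolled approximately 29% were responders" that about 71% of patients sit below 12%. That figure comes from another study, its responder definition is not given, and nothing ties it to PPV/SVV. In Set B it serves only as an assumed mixing weight.
- A reader might infer that clear responders are removed in bulk. In Set B, 62-93% of responders at 8 ml/kg and 58-84% at 6 ml/kg keep an AUC, because many start high and fall across the line.
- A reader might infer that the means will flatter RPVi. The direction of bias is not fixed; the fault is that the means are not representative.

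**What to change.** For the validation set, replace the mean of individual values in section 8 with:

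1. A single AUC across all patients. Use either one RPVi and one PPV/SVV value per patient from a common, stated window, or all cycles pooled with patient-clustered bootstrap intervals.
2. A single kappa across all patients, at one RPVi threshold fixed in the first group. This matches what sections 4.1 and 8 say the first group is for.
3. Any within-patient ROC or kappa as descriptive only, reporting by tidal-volume group how many patients could not be computed.

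The cost is SAP wording and a reanalysis of data already to be recorded; no new data are needed.

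There are two real downsides. The question moves from tracking within a patient to discrimination across patients, and the SAP should say so. The interval will also be wide, especially within a tidal-volume group if few patients exceed 12%. Under Set B at 6 ml/kg the assumed means are 10.5 ± 3 and 6 ± 2.25, so the share above 12% before the bolus is 0.29 × 0.31 + 0.71 × 0.004 ≈ 0.09, or about 2 of 25 patients. An AUC for that group alone would then say little.
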